7.1.1 PSA Response Rate

[figure not shown]
Per PCWG3 criteria, PSA response rate will be defined as the proportion of subjects who have PSA response as defined by at least 50% decline in PSA level from baseline measured twice at least 3 weeks apart. Based on the PCWG3 criteria, a favorable effect on PSA may be delayed for \geq 12 weeks. PSA will be monitored every 4 weeks, but treatment will be planned to continue through early rises for 12 weeks unless other evidence of progression, such as radiographic progression.

Therefore, early rises in PSA before 12 weeks will not be considered when determining PSA response.

7.1.2 Criteria for PSA Progression

For rising PSA after an initial decline from baseline, the PSA is recorded from the start of therapy to first PSA increase that is \geq 25% and \geq 2ng/mL above the nadir, which is confirmed by a second value 4 or more weeks later, confirming a rising trend. If there is no initial decline from baseline, PSA progression is defined as \geq 25% increase and \geq 2 ng/mL increase from baseline beyond 12 weeks.

Patients who have only documented PSA progression in the absence of radiographic or clinical progression may continue on study therapy.

7.1.3 Duration of Response

Duration of overall response: The duration of overall response is measured from the time measurement criteria are met for PSA response until the first date that PSA progression is documented, or if there is interval development of recurrent or progressive disease objectively documented by RECIST 1.1 criteria.

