7.1.4 Progression-Free Survival

PSA progression-free survival (PSA-PFS) is defined as the duration of time from start of treatment to time of PSA progression as defined above in section 7.1.2 or death, the event that occurs first. Patients who have not experienced either event at the time of analysis will be censored at the last PSA measurement date.

Radiographic progression-free survival (rPFS) is defined as the duration of time from start of treatment to time of radiographic progression as defined above in section 7.1.5 or death, the event that occurs first. Patients who have not experienced either event at the time of analysis will be censored at their last radiographic scan date.

Progression-Free Survival (PFS) is defined as the duration of time from start of treatment to time of first PCWG3 defined progression or death, the event that occurs first. Patients who have not experienced either event at the time of analysis will be censored at the date of their last progression assessment.

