7.1.5 Radiographic Response Criteria

All radiographic response criteria are as per PCWG3 criteria summarized below.

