7.5 Duration of Response - Non prostate malignancies

Duration of overall response: The duration of overall response is measured from the time measurement criteria are met for CR or PR (whichever is first recorded) until the first date that recurrent or progressive disease is objectively documented (taking as reference for progressive disease the smallest measurements recorded since the treatment started).

The duration of overall CR is measured from the time measurement criteria are first met for CR until the first date that recurrent disease is objectively documented.

Duration of stable disease: Stable disease is measured from the start of the treatment until the criteria for progression are met, taking as reference the smallest measurements recorded since the treatment started.

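### Duration of response does not count death and has no censoring rule, so Kaplan-Meier DOR is biased upward if responders die without documented progression; in mCRPC its imaging trigger also differs from that of rPFS and PFS

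*Combined protocol and SAP*

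**What the plan says.** **DOR, mCRPC (section 7.1.3).** The start is defined thus: "The duration of overall response is measured from the time measurement criteria are met for PSA response". There are two end events. The first is PSA progression: "until the first date that PSA progression is documented". The second is "interval development of recurrent or progressive disease objectively documented by RECIST 1.1 criteria". Death is not listed.

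**DOR, Cohort B (section 7.5).** Response runs "until the first date that recurrent or progressive disease is objectively documented". Death is again not listed.

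**PFS-type endpoints (section 7.1.4).** All three count death and give a censoring date:
- PSA-PFS runs to "time of PSA progression as defined above in section 7.1.2 or death, the event that occurs first".
- rPFS runs to "time of radiographic progression as defined above in section 7.1.5 or death, the event that occurs first".
- PFS runs to "time of first PCWG3 defined progression or death, the event that occurs first".

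Section 7.6 does the same for both Cohort B PFS endpoints.

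**Imaging criteria, mCRPC (section 7.1.5).** "All radiographic response criteria are as per PCWG3 criteria summarized below". Within that summary, nodal and visceral disease follow RECIST 1.1 with caveats (7.1.5.1, 7.1.5.2), and bone follows the 2+2 rule (7.1.5.3).

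**Analysis (section 11.3).** DOR among responders is reported by Kaplan-Meier, with the median if reached and the 52-week event-free proportion. No section gives a censoring date for DOR or says what happens to a responder who dies without progression.

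**The concern.** Kaplan-Meier recognises only events and censored observations. If death is not an event, a responder who dies before progression is documented can only be censored. The curve then treats that patient as having the same prospects of continued response as those still alive and followed. This lengthens DOR relative to a definition that counts death, as the PFS-type endpoints do.

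The protocol leaves room for such deaths. The schedule in section 6.1 shows no imaging at end of treatment or in follow-up, follow-up contact may be by telephone, and survival status is collected every 3 months. For a responder who has stopped treatment, death may therefore be recorded more reliably than progression. Section 7.4.3 also foresees symptomatic deterioration without objective progression.

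The second issue is separate. In mCRPC, the imaging part of DOR cites a different standard from rPFS and PFS, so the same scan series can give different progression dates for endpoints that will be read together. In a small single-arm trial, durability will be read alongside the response rate, and few patients contribute to it.

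**Working it through.** **No DOR figure to reproduce.** The documents state no DOR assumption, so the size can only be illustrated. The response-rate sizing was checked as background, by exact binomial calculation:
- Cohort A (at least 2 of 15, then at least 6 of 25): type I error 0.033, power 0.802.
- Cohort C (at least 6 of 25): 0.033 and 0.807.
- Cohort B (at least 3 of 15): 0.036 and 0.764.

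These agree with the stated 80%, 80% and 76% power, and DOR plays no part in them.

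**Responders entering the DOR analysis at the target rates (section 11.1).** Cohorts A and C: 25 × 0.30 = 7.5 each. Cohort B: 15 × 0.25 = 3.75.

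**Effect of censoring deaths.** Assumptions, none from the documents: constant hazards; true median m (death counted) of 6, 9 or 12 months; share s of first events that are deaths without documented progression, from 5% to 30%.
- Total hazard: λ = ln 2 / m. Progression hazard: (1−s)λ.
- Median with deaths censored: ln 2 / [(1−s)λ] = m/(1−s).
- 12-month (about 52-week) proportion: 2^(−12/m) with death counted, 2^(−12(1−s)/m) with deaths censored.
- Example, m = 6 and s = 0.30: 6/0.70 = 8.57 months; 2^(−1.4) = 37.9% against 2^(−2) = 25.0%.

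| True median; 12-month proportion | s = 5% | s = 10% | s = 20% | s = 30% |
|---|---|---|---|---|
| 6 months; 25.0% | 6.3; 26.8% | 6.7; 28.7% | 7.5; 33.0% | 8.6; 37.9% |
| 9 months; 39.7% | 9.5; 41.6% | 10.0; 43.5% | 11.3; 47.7% | 12.9; 52.4% |
| 12 months; 50.0% | 12.6; 51.8% | 13.3; 53.6% | 15.0; 57.4% | 17.1; 61.6% |

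At s = 0 nothing changes.

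**One death among eight responders (invented times: 3, 5, 6, 8, 10, 13, 16, 20 months).** With all eight as events, the median is 8 months and the 12-month proportion 3/8 = 37.5%. Censoring one patient at the time of death removes one factor from the Kaplan-Meier product:
- Death at 3 months: 0.375/(7/8) = 42.9%, median 10.
- Death at 8 months: 0.375/(4/5) = 46.9%, median 10.
- Death at 10 months: 0.375/(3/4) = 50.0%, median still 8.
- Death at 13 months or later: neither figure changes.

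**Imaging trigger, mCRPC, side by side.**
- *Nodes and viscera:* both routes rest on RECIST 1.1; section 7.1.5 adds caveats on lesion size and recording.
- *Bone:* section 7.1.5.3 needs at least two new lesions on the first post-treatment scan plus at least two more on the next, and dates progression to the earlier scan. RECIST progression in section 7.4.1 needs one or more new lesions.
- *Direction:* section 7.1.3 does not say whether new bone-scan lesions count as RECIST new lesions. If they do, a single new bone lesion ends DOR but not rPFS, and DOR is shorter. If they do not, a confirmed 2+2 bone progression ends rPFS but not DOR, and DOR is longer.

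**The case against.** The strongest reply is that a progression-only DOR may be intended. Sections 2.5.3 and 11.3 list time to progression and time to PSA progression beside PFS and PSA-PFS, so measures with and without death are meant to coexist. Censoring at death is an inference, because no DOR censoring rule is written. PSA is measured about every 4 weeks on treatment, so progression may usually be recorded before death. Deaths also remain visible in PFS, rPFS and OS, and DOR is descriptive, with no test.

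Much of this limits the size. Frequent PSA testing argues for the low end of the range, and the documents give no basis for assuming a high share of such deaths. It does not remove the gap. If death is not an event, Kaplan-Meier offers nothing but censoring, and a deliberate progression-only choice would still need a stated rule for deaths.

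Three stronger readings are tempting, and the documents do not support them:
- *That mCRPC DOR ends on RECIST 1.1 alone.* PSA progression is the first-named end event, and section 7.1.2 defines it for PSA-PFS as well.
- *That the RECIST/PCWG3 mismatch also inflates DOR.* Its direction is not fixed. Only the omission of death supports an upward bias.
- *That DOR conflicts with every other endpoint.* Time to progression is named but not defined, so the difference on death is shown only against PSA-PFS, rPFS and PFS.

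**Conclusion.** The point stands. As written, DOR in 7.1.3 and 7.5 gives a responder who dies without documented progression no event, unlike PSA-PFS, rPFS and PFS, and Kaplan-Meier DOR is then biased upward.

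The size rests on the assumed death share and on constant hazards. At 5% the effect is minor: the median rises by about 5% and the 12-month proportion by about 2 points. At 30% the median rises by about 43% (1/0.70 = 1.43) and the proportion by about 12 to 13 points. With only about 7 to 8 responders in each mCRPC cohort and about 4 in Cohort B, one death can move the estimates or leave them unchanged, depending on when it occurs.

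The imaging mismatch in mCRPC is real but narrow: mainly bone and confirmation, with no fixed direction. A reader might infer that the trial's main conclusion is at risk. It is not, because the PSA and RECIST response decision rules do not use DOR. This should be corrected before analysis, but it is not a flaw in the primary design.

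**What to change.** - **Section 7.1.3:** end DOR at the first of PSA progression (7.1.2), radiographic progression per 7.1.5 (PCWG3), or death.
- **Section 7.5:** add death as an end event, whichever occurs first.
- **Both sections:** censor responders without an event at their last progression assessment, as for PFS.

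If a progression-only measure is also wanted, time to progression is already listed in 11.3 and can serve once it is defined with its own rule for deaths.

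The cost is a sentence or two in each section. Survival status, PSA and imaging are already in the schedule, so no new data are needed. The downside is that reported DOR may be shorter. Sample size and decision rules do not change.

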7.1.4 Progression-Free Survival

PSA progression-free survival (PSA-PFS) is defined as the duration of time from start of treatment to time of PSA progression as defined above in section 7.1.2 or death, the event that occurs first. Patients who have not experienced either event at the time of analysis will be censored at the last PSA measurement date.

Radiographic progression-free survival (rPFS) is defined as the duration of time from start of treatment to time of radiographic progression as defined above in section 7.1.5 or death, the event that occurs first. Patients who have not experienced either event at the time of analysis will be censored at their last radiographic scan date.

Progression-Free Survival (PFS) is defined as the duration of time from start of treatment to time of first PCWG3 defined progression or death, the event that occurs first. Patients who have not experienced either event at the time of analysis will be censored at the date of their last progression assessment.

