5.0 TREATMENT PLAN

5.1 Treatment Dosage and Administration

Protocol treatment must start within 14 business days of enrollment to the study.

- 5.1.1 In this study, Cohort A and Cohort B patients will start treatment with nivolumab dosed at 3 mg/kg IV and ipilimumab 1 mg/kg every 3 weeks for up to 4 doses. Cohort C patients will receive immunotherapy with nivolumab dosed at a flat dose of 480 mg IV every 4 weeks for up to 26 doses or 104 weeks.
- 5.1.2. Cohorts A and B maintenance immunotherapy with nivolumab dosed at a flat dose of 480 mg IV every 4 weeks will be continued for up to 23 doses or 92 weeks. Missed doses of 480 mg Nivolumab due to toxicity or general health condition will be skipped.

5.1.3 Total protocol therapy for all Cohorts will be up to 104 weeks during treatment. If disease progression or recurrence occurs during the follow-up phase, then per treating physician discretion, the patient may resume nivolumab 480 mg IV every 4 weeks until progression if tolerated with axial imaging as per protocol every, 12 weeks.

5.1.4 All study therapy will be administered on an outpatient basis.

Agent	Precautions	Dose	Route	Schedule	Cycle Length
Nivolumab (solution for injection) induction Cohort A and B only	Administer before other immunotherapy agents	3 mg/kg up to 4 doses	IV infusion over 30 minutes, +/- 10 minutes, with a sterile, nonpyrogenic, low protein binding 0.2 to 1.2 micrometer in-line filter. Follow with saline flush.	Day 1	3 weeks
Ipilimumab (solution for injection) induction Cohort A and B only	Administer 30 minutes after nivolumab.	1 mg/kg up to 4 doses	IV infusion over 90 minutes, +/- 10 minutes, through a non-pyrogenic, low protein-binding in-line filter. Separate IV line required.	Day 1	3 weeks
Nivolumab (solution for injection) maintenance After induction in Cohorts A and B; and throughout in Cohort C	Administer before other immunotherapy agents	480 mg up to 23 doses (92 weeks in Cohort A and B, and 104 weeks in Cohort C)	IV infusion over 30 minutes, +/- 10 minutes, with a sterile, nonpyrogenic, low protein binding 0.2 to 1.2 micrometer in-line filter. Follow with saline flush.	Day 1	4 weeks

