5.6 Duration of Follow-Up

Patients will be followed every 3 months for 24 months after removal from treatment or until death, whichever occurs first. Patients removed from treatment for unacceptable adverse events will be followed until resolution or stabilization of the adverse event.

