6.0 STUDY PROCEDURES

6.1 SCHEDULE OF ASSESSMENTS:

	Screening (within 28 days)	C1D1	C2D1	C3D1	C4D1	D1C5+	EOT¹²	Follow Up⁸
Informed Consent	X							
Review Eligibility Criteria	X							
Demographics, Height	X							
Prior and Concomitant Medications	X	X	X	X	X	X	X	
Review Adverse Events¹⁰	X	X	X	X	X	X	X	
Physical Examination, Vital Signs¹, Weight	X	X	X	X	X	X	X	
ECOG Performance Status	X	X	X	X	X	X	X	
Survival Status								X Q3m
Laboratory Assessments								
Pregnancy Test for WOBCP²	X							
CBC with diff, platelets³	X	X	X	X	X	X	X	
Comprehensive Metabolic Panel, including Alk Phos⁴	X	X	X	X	X	X	X	

	Screening (within 28 days)	C1D1	C2D1	C3D1	C4D1	D1C5+	EOT ¹²	Follow Up ⁸
LDH	X	X	X	X	X			
PSA¹¹	X	X	X	X	X	X	X	X
Testosterone¹¹	X				X		X	
TSH, free T3, free T4 (If Clinically Indicated: FSH, LH, ACTH)	X	X	X	X	X	X ⁶	X	
Therapy								
Cohorts A and B Nivolumab 3 mg/kg IV q3 wks for up to 4 doses¹³				X				
Cohorts A and B Ipilimumab 1 mg/kg IV q3 wks for up to 4 doses¹³				X				
Cohorts A and B Nivolumab 480 mg IV q4 wks for up to 23 doses¹³						X		
Cohort C Nivolumab 480 mg IV q4 wks¹⁴				X		X		
Imaging Tumor Assessments								
CT chest	X					X (q 12 wks)		
CT Abdomen/Pelvis or MRI Abdomen/Pelvis⁵	X					X (q 12 wks)		
Tc^{99m} Bone Scan (prostate only)	X					X (q 12 wks)		
QoL: BPI-SF and EORTC QLQ C30	X					X (q 12 wks)		
Correlatives								
Tumor Tissue Archival (CRPC preferred if available)	X							
Tumor Biopsy	X						X ⁷	
Research blood⁹		X	X	X		X (q 12 wks)	X	

1. Vital signs will include temperature, pulse, respirations, blood pressure; height will be obtained at screening only.
2. WOCBP: Women of child bearing potential; urine or serum pregnancy test.
3. CBC with diff includes total WBC, hemoglobin, hematocrit and differential of the WBC including absolute counts.
4. COMP or Comprehensive metabolic profile includes sodium, potassium, chloride, bicarbonate, BUN, creatinine, AST, ALT, alkaline phosphatase, total bilirubin.
5. With or without intravenous contrast, before or on associated visit. CT or MRI (preferred) brain with or without IV contrast if suspected or known brain metastases. Frequency of tumor assessments will be q12 weeks.
6. Every 42 calendar days ± 14 business days. May be delayed if infusion is not scheduled within the window.
7. Optional tissue biopsy collection at progression if subject consents; +/- 14 working days.
8. Follow up with phone call or with clinic visit.

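### No scan is scheduled after treatment stops, yet later deaths count as rPFS and PFS events, so the reported 52-week rPFS is likely biased, usually but not always upward

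*Combined protocol and SAP*

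**What the plan says.** **Scans.** In the Section 6.1 table the CT, MRI and bone scan rows are marked at screening and from cycle 5 day 1 onward; the end-of-treatment and follow-up cells are empty. Footnote 5 gives the interval: "Frequency of tumor assessments will be q12 weeks".

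**Follow-up.** Section 5.6: "Patients will be followed every 3 months for 24 months after removal from treatment or until death, whichever occurs first". Footnote 8 of Section 6.1 allows a phone call or a visit. The follow-up column holds survival status and PSA, and footnote 11 restricts PSA to Cohort A.

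**rPFS.** Section 7.1.4 runs it to "time of radiographic progression as defined above in section 7.1.5 or death, the event that occurs first"; those with neither "will be censored at their last radiographic scan date". Section 7.6 applies the same rule to Cohort B.

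**PFS.** For prostate patients it runs to "time of first PCWG3 defined progression or death, the event that occurs first" and is censored at the last progression assessment. For Cohort B it adds clinical progression.

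**Duration of response.** For prostate patients it runs "until the first date that PSA progression is documented" or RECIST progression is found (Section 7.1.3). For Cohort B it runs "until the first date that recurrent or progressive disease is objectively documented" (Section 7.5). Neither definition counts death.

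**Progression in follow-up.** Section 5.1.3 foresees it: "If disease progression or recurrence occurs during the follow-up phase, then per treating physician discretion, the patient may resume nivolumab", with 12-weekly imaging for those who resume.

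**Reporting.** Section 11.3 gives the Kaplan-Meier median and the 52-week event-free proportion, overall and by cohort.

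**The concern.** The scan schedule stops with treatment, but the event definition does not. Someone who leaves treatment for toxicity, intercurrent illness or by choice, without radiographic progression, has no planned route to a progression date. If that patient progresses and later dies within the 24-month follow-up, the death date stands in for the progression date. If the patient survives, follow-up time ends at the last on-treatment scan.

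The group is foreseeable: Section 5.2 discontinues patients for repeated grade 3 or any grade 4 toxicity and for toxicity delays beyond 84 days, and Section 5.4 adds other reasons. At stake is the 52-week rPFS proportion. The distortion may also differ between Cohorts A and C if the two regimens differ in how many patients stop for toxicity.

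**Working it through.** The plan gives no assumed rate, event count or power for rPFS, PFS or duration of response, so there is no figure of its own to reproduce.

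**1. What each patient contributes to rPFS under the rules as written**

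| Patient | Contribution |
|---|---|
| Radiographic progression on treatment | Event at that scan (unaffected) |
| Stops without it, dies in follow-up | Event at death, however long after the last scan |
| Stops without it, alive | Censored at last on-treatment scan |
| Stops before cycle 5 day 1, alive | Possibly censored at the screening scan, so no time at risk |

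By the cycle lengths in footnotes 13 and 14, cycle 5 day 1 falls at 4 × 3 = 12 weeks in Cohorts A and B and at 4 × 4 = 16 weeks in Cohort C, if there are no delays.

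**2. Does other text supply a schedule?** No. The Section 5.4 instruction to keep scanning covers treatment delays. The Section 7.4.3 note asks for effort to document progression after symptomatic deterioration but sets no dates. Section 5.1.3 schedules imaging only once nivolumab has been resumed.

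**3. Size.** Simulation of 100,000 patients per scenario, 81 scenarios (27 per correlation). Inputs from the plan: 12-weekly scans, the event and censoring rules above, and 24 months of survival follow-up. Assumed inputs, none from the documents:

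- median time to progression 12, 26 or 52 weeks
- median survival after progression 26, 52 or 78 weeks
- 10%, 30% or 50% stopping without progression by week 52
- correlation between stopping time and progression time -0.5, 0 or +0.5
- death hazard before progression 0.001 per week

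The estimate is S(52) = Π(1 - d/n) over event times up to week 52, where d is the number of events and n the number at risk. Bias = S(52) under the plan's rule minus S(52) for the same patients scanned 12-weekly through follow-up.

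| Median to progression / survival after it (weeks) | Stopping by week 52 | Correlation | Scans continued | Plan's rule | Bias (points) | Bias with late deaths censored (points) |
|---|---|---|---|---|---|---|
| 26 / 52 | 30% | 0 | 26.5% | 30.1% | +3.6 | -0.7 |
| 26 / 52 | 30% | +0.5 | 26.5% | 31.8% | +5.3 | +2.6 |
| 26 / 52 | 30% | -0.5 | 26.5% | 26.3% | -0.2 | -6.3 |
| 26 / 78 | 50% | +0.5 | 26.5% | 36.9% | +10.4 | +5.3 |
| 52 / 78 | 50% | -0.5 | 50.2% | 44.7% | -5.5 | -11.1 |

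Differences are taken before rounding. The last column censors at the last scan when death comes more than 24 weeks (two scan intervals) later.

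Ranges over all scenarios:

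- correlation 0: +0.3 to about +8.6 (the upper end varied from 8.4 to 8.6 between runs)
- correlation +0.5: +0.7 to +10.4
- correlation -0.5: -5.5 to +8.5

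**4. Why the sign can change.** Missed progressions leave patients in the risk set until death, which raises the curve. Survivors are removed at their last scan; if they would have progressed late, those left at risk are the earlier progressors, which lowers it.

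**5. Duration of response.**

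- *Cohort A:* can still end on PSA progression, because PSA is marked at end of treatment and in follow-up.
- *Cohort B:* needs objective documentation, and none is scheduled after stopping.
- *Cohort C:* footnote 11 leaves no scheduled PSA, although Sections 7.1 and 11.3 treat PSA as part of that cohort's assessment. The gap applies as far as the footnote stands.

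**The case against.** Several stronger readings are tempting, and the documents do not support them.

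- *Progression after stopping is unobservable, or its scans are not collected.* The plan only fails to schedule scans. Sections 5.1.3 and 7.4.3 both expect some progression to be found after treatment. Equally, Section 5.1.3 does not say how it is found, so one cannot assume that sites will hold the images.
- *Responders who stop for toxicity cannot contribute to duration of response.* Untrue for Cohort A, and in any cohort a censored responder contributes time at risk. Late deaths play no part, since death is not an event for this endpoint.
- *PFS suffers exactly as rPFS does.* Cohort A's follow-up PSA may count towards PCWG3 progression, and Cohort B's PFS includes clinical progression, which a follow-up visit could reveal. PFS is only partly affected.
- *The bias is certainly upward.* Step 3 shows it can be negative.
- *The plan's analysis and the 24-week censoring analysis bracket the truth.* They roughly do when stopping is unrelated to progression. At correlation +0.5 both lay above it in all 27 scenarios; at -0.5 both lay below it in 13 of 27.
- *Patients completing 104 weeks add to the problem.* They have scans past week 52 and cannot move the 52-week figure.

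The best remaining defence is proportion. These endpoints are secondary and carry no decision rule. With 25 patients and a 25% proportion, the approximate 95% half-width is 1.96 × √(0.25 × 0.75 / 25) = 0.17, or 17 points, wider than any bias found here. That limits the severity. It does not remove the point, because the interval does not account for bias and the repair is cheap.

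**Conclusion.** The gap is real: post-treatment scans are unscheduled, while deaths in the 24-month follow-up count without limit on time since the last scan. The 52-week rPFS proportion is likely distorted, usually upward. Both the size and the sign depend on assumed progression, survival and stopping rates and on who stops early; the documents settle none of these. PFS is affected to a lesser degree. Duration of response is affected in Cohort B, and conditionally in Cohort C. The PSA-response primary endpoint, its decision rules and the sample size are untouched. The change is worth making but is not critical.

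**What to change.** 1. At the existing 3-monthly contact, for patients who stopped without radiographic progression, record the date and result of any standard-care scan until radiographic progression. Use these scans in rPFS, PFS and duration of response.
2. Record the start date of any new anticancer therapy, and state in Section 11.3 how scans after that date are handled, so that next-line effects do not enter unnoticed.
3. Add one rPFS/PFS sensitivity analysis that censors at the last scan when death comes more than 24 weeks later. Report it beside the main analysis as a sensitivity check, without claiming that the two bracket the truth.

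Cost: a few case report form fields and one extra analysis; no added scans or visits. Downside: standard-care scans come at irregular times and may follow symptoms, so progression dates after stopping will be less regular than those on treatment.
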